5. Willingness to utilize two reliable forms of contraception (for both males and females of childbearing potential) from Screening to one month after the last dose of study drug

Key Exclusion Criteria:

1. Known active infection with hepatitis B virus (HBV) and/or human immunodeficiency virus (HIV)
2. History of renal transplant and/or severe renal impairment defined as eGFR (estimated glomerular filtration rate) of less than 30 mL/min/1.73 m²
3. Evidence of tumor burden >Milan criteria, or evidence of micro- or macrovascular invasion in explanted liver
4. Hepatocellular carcinoma (HCC) at entry into the study
5. Concurrent sirolimus (rapamycin) use

Title: A Multicenter, Double-Blind, Randomized Trial of IDN-6556 in Subjects Who had Hepatitis C Virus (HCV) Reinfection and Liver Fibrosis or Cirrhosis following Orthotopic Liver Transplantation for Chronic HCV Infection and Who Subsequently Achieved a Sustained Virologic Response Following anti-HCV Therapy

6. History or presence of clinically concerning cardiac arrhythmias, or prolongation of Screening (pre-treatment) QTcF interval of > 480 milliseconds (msec)
7. Subjects with diagnosed or suspected systemic lupus erythematosus (SLE) and/or rheumatoid arthritis (RA)
8. If female: known pregnancy, positive urine or serum pregnancy test, or lactating/breastfeeding.

Criteria for Evaluation:**Safety Variables:**

Safety evaluations will be based on adverse event (AE) reports. These will be coded using MedDRA to preferred terms, sorted by body system, and compared between the two treatment groups.

1. Serious adverse events will be analyzed separately
2. Clinical laboratory variables will be evaluated in the context of coinciding clinical adverse events when necessary

Efficacy Variables:Efficacy Endpoints:

- Ishak Fibrosis Score
- Necro-inflammatory sub-score of the modified Histological Activity Index
- Biomarkers of apoptosis
- Liver function (e.g., ALT, AST, bilirubin)
- Transient elastography (to be performed at select centers only)

Exploratory Endpoint:

- Morphometric image analysis to quantify collagen deposition

Statistical Methods:

All endpoints will be tested at a two-sided statistical significance level of 0.05.

For the comparison of Ishak Fibrosis Scores at 24 months, subjects will be classified into one of the following three categories:

- Category 1. Regression at 24 months defined as a greater than or equal to a one point improvement in Ishak Fibrosis Score from Baseline.

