3. If the estimated absolute increase in the proportion of subjects who show regression in Ishak Fibrosis Score is at least 15%, (e.g., an estimated increase from 30% to greater than 45%), then the IDN-6556 regimen will be evaluated definitively in a subsequent Phase 3 study.

The operating characteristics for this three-category decision guideline (based on 100,000 simulated trials) are shown in the table below.

Table 12.1 Probabilities of Study Outcomes According to Various Levels of True Treatment Effect (TE)

| TE | Probability of obtaining an estimated TE (active – placebo) | | |
|----|---|-----------------|------|
| | <5% | Of >5% but ≤15% | >15% |
| 0 | 67% | 22% | 11% |
| 5 | 52% | 26% | 22% |
| 10 | 36% | 27% | 37% |
| 15 | 23% | 24% | 53% |
| 20 | 13% | 19% | 68% |
| 25 | 7% | 13% | 80% |
| 30 | 3% | 8% | 89% |

Of note:

1. The false-positive error rate of the screening procedure is low. In particular, if the IDN-6556 regimen truly provides no improvement in the 2-year Ishak Fibrosis Score, then there is only an 11% chance of going forward to a Phase 3 study and only a 2.5% chance of false positive conclusion that the IDN-6556 regimen has statistically significant improvement in efficacy relative to placebo.
2. The false-negative error rate is acceptable. If the IDN-6556 regimen truly provides an absolute increase of 15%, (e.g., an increase from 30% to 45%), then there is only a 23% chance that the combination intervention would be discarded, and thus a 77% chance that it would be evaluated in a subsequent Phase 3 study. If the true absolute increase is 15%, there is a 20% chance that the IDN-6556 regimen will have a statistically significant improvement in efficacy relative to placebo and a 80% chance of a statistically significant difference if the true absolute increase is 37% (at the 2-sided 0.05 level).

Title: A Multicenter, Double-Blind, Randomized Trial of IDN-6556 in Subjects Who had Hepatitis C Virus (HCV) Reinfection and Liver Fibrosis or Cirrhosis following Orthotopic Liver Transplantation for Chronic HCV Infection and Who Subsequently Achieved a Sustained Virologic Response Following anti-HCV Therapy

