3.3 RANDOMIZATION

The assignment to emricasan or placebo will be performed randomly in a 2:1 ratio to emricasan 25 mg BID or matching placebo BID. Approximately 60 subjects will be enrolled in this trial with 40 assigned to emricasan and 20 assigned to placebo. Randomization will be stratified based on baseline Ishak Fibrosis Score: F2, F3-F5, or F6.

The randomization schedule will be generated using a validated randomization program and verified for accuracy using strict quality control procedures. Randomization numbers and study drug assignment will be centrally coordinated through the study's Interactive Web Randomization System (IWRS).

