4 PLANNED SIZE DETERMINATION

This study will be conducted at multiple centers at which approximately 60 subjects will be enrolled and treated in a 2:1 ratio with emricasan or placebo, respectively. The sample size determination for this study is based on the Phase 2b screening methodology presented in [Fleming and Richardson \(2004\)](#).

The base case for the placebo response rate of 30% was assumed and obtained from [George, et al \(2009\)](#), where it stated that 29% of patients showed a response in fibrosis from a mean of 1.6 years following HCV-SVR.

Treatment duration for all subjects is expected to be two years. The primary analysis of this Phase 2 “screening” study is formally based on a three-category decision guideline. The decision guideline for this study is based on whether the difference in the proportions of subjects who show a response (i.e., improvement or no change) per their Ishak Fibrosis Score at 24 months for emricasan compared to placebo is less than 5%, is from 5% up to 15%, or is more than 15%. Specifically, the outcome of the study will determine one of the following three course of action:

1. If the difference in response rates between emricasan and placebo (i.e., emricasan response rate – placebo response rate) is less than 5%, then emricasan regimen is not plausibly more efficacious than placebo; hence, emricasan or its utility in this indication will be reconsidered.
2. If the difference in response rates between emricasan and placebo is from 5% up to 15%, then emricasan is plausibly more efficacious than placebo in this indication if secondary analyses of biomarkers suggest utility of emricasan or a positive safety profile is observed; hence, emricasan could be evaluated in a subsequent Phase 3 clinical study.
3. If the difference in response rates between emricasan and placebo is more than 15%, then emricasan could be evaluated in a subsequent Phase 3 study.

These categories should not be interpreted as providing strict decision rules but rather as guidelines that will be factored into a broader scientific assessment of the benefit to risk profile for emricasan in this indication. This broader assessment will include consideration of secondary efficacy analyses, safety profile, and relevant information external to this study.

The operating characteristics for this three-category decision guideline are shown in Table 1.

Table 1. Operating Characteristics for Three-Category Decision Guideline

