5 STUDY ENDPOINTS

5.1 PRIMARY EFFICACY ENDPOINT

The Ishak Fibrosis Score will be determined by liver biopsy as scored by the central histopathologist. The Ishak Fibrosis Score classification is defined as:

- 0 = No fibrosis (F0);
- 1 = Fibrous expansion of some portal areas, with or without short fibrous septa (F1);
- 2 = Fibrous expansion of most portal areas, with or without short fibrous septa (F2);
- 3 = Fibrous expansion of most portal areas, with occasional portal to portal bridging (F3);
- 4 = Fibrous expansion of portal areas, with marked bridging (F4);
- 5 = Marked bridging with occasional nodules (F5);
- 6 = cirrhosis probable or definite (F6).

Fibrosis scores of F0 and F1 will be excluded from enrollment. The change from baseline in the Ishak Fibrosis Score will be derived for each subject and will be used to classify subjects into one of the three following groups:

- Improvement, defined as having a reduction from baseline of at least 1-point in the Ishak Fibrosis Score
- Stable, defined as having no change from baseline in the Ishak Fibrosis Score
- Worsening, defined as having an increase from baseline in the Ishak Fibrosis Score

Subjects will be classified as a responder or non-responder based on the above three groups and their baseline Ishak Fibrosis score. The definition of response is based on the following:

- For subjects with baseline Ishak Fibrosis Score of F2-F5, achieving either improvement or remaining stable
- For subjects with baseline Ishak Fibrosis Score of F6, achieving improvement

The response at Month 24 will be used as the primary endpoint in this study. Response rates at Month 12 using the same definitions as above will also be summarized.

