9.1 PRIMARY EFFICACY ANALYSIS

All screening and post-baseline biopsy data collected will be used in the primary analysis, irrespective of the defined protocol visit window. Classification of the Ishak fibrosis score will be summarized descriptively by treatment group at baseline, Month 12, and Month 24. Response at Months 12 and 24 will be summarized descriptively by treatment group, along with exact (Clopper-Pearson) 95% confidence intervals (CIs). The risk difference between groups will also be provided with its 95% CI.

For the primary efficacy analysis based on the Month 24 biopsy, subjects with a missing Month 24 biopsy will have their Ishak fibrosis score imputed. Imputation of missing Ishak fibrosis scores will be conducted using multiple imputation (MI). Results will be imputed based on age, gender, baseline Ishak fibrosis score, and the Month 12 Ishak fibrosis score. Imputations will be based on at least 5 imputed datasets, depending on the percent of missing observations and will be documented in the clinical study report. Within each imputed dataset, the change from baseline at Month 24 will be derived to allow categorization into response or no response as defined in [Section 5.1](#).

Study success will be determined per the criteria described in [Section 0](#). This primary analysis will be conducted using the FAS.

The following sensitivity analyses will be provided for the primary efficacy endpoint, using different methods for the handling of missing liver biopsy results at Month 24:

- All FAS observed post-baseline biopsies
- All FAS observed post-baseline at Month 24 (within the sensitivity analysis visit window, per [Section 3.5](#))
- FAS with missing M24 biopsy imputed to ‘No’ response
- Per-protocol

Response rates at Month 12 will be summarized using the FAS in the same manner as the response rates at Month 24 (i.e., using MI). Subjects with a missing Month 12 liver biopsy will have their Month 12 Ishak fibrosis score imputed based on age, gender, and baseline Ishak fibrosis score.

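### SAP 9.1 reports the primary risk difference and its 95% CI without the randomisation strata, so the interval is conservative if response rates differ by stratum and does not match the stratified test in 9.2.1

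*SAP*

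**What the plan says.** - **Randomisation (SAP 3.3).** "Randomization will be stratified based on baseline Ishak Fibrosis Score: F2, F3-F5, or F6". The planned split is 40 to emricasan and 20 to placebo, with at most 15 F6 subjects (SAP 3.2).
- **Response (SAP 5.1).** F2-F5 subjects respond if they improve or stay the same. The rule for F6 is stricter: "For subjects with baseline Ishak Fibrosis Score of F6, achieving improvement".
- **Primary analysis (SAP 9.1).** Response rates get Clopper-Pearson intervals. For the comparison: "The risk difference between groups will also be provided with its 95% CI". No interval method, stratification or rule for combining intervals over imputations is given. Success is judged by the three-category guideline of SAP section 4, which compares the point difference with 5% and 15%.
- **Test (SAP 9.2.1).** A Cochran-Mantel-Haenszel (CMH) test accompanies each analysis in 9.1, stratified in turn by the randomisation strata and by two other baseline groupings.
- **Protocol 12.6.3.** The primary model was an ordinal logistic regression whose first adjustment variable was baseline Ishak score. SAP 14.1 says the primary analysis was updated to the response endpoint, but not that this adjustment was dropped.

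**The concern.** Stratified randomisation removes between-stratum variation from the treatment difference. A standard error computed as if there were no strata puts that variation back. Here the stratum probably predicts response by construction, because staying stable counts as response up to F5 but not at F6, and protocol 4.2 expects fibrosis to stabilise or regress in most subjects.

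At stake is the only interval planned for the primary treatment comparison, in a trial of about 60 subjects. That interval may be wider than the design warrants, and it may disagree with the stratified test reported beside it. Where biopsies are missing, the crude difference also picks up chance imbalance in the strata.

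**Working it through.** **1. The plan's own figures.** Inputs: "Approximately 60 subjects will be enrolled in this trial with 40 assigned to emricasan and 20 assigned to placebo" (SAP 3.3); "The base case for the placebo response rate of 30% was assumed" (SAP 4); two-sided 0.05 (protocol synopsis). Protocol 12.5 states 20% power at +15 points and 80% at +37. With pooled SE₀ under the null and unpooled SE₁, power = Φ[(Δ − 1.96·SE₀)/SE₁].
- Δ = 0.15: pooled rate 0.40; SE₀ = √(0.40·0.60·0.075) = 0.134; SE₁ = √(0.45·0.55/40 + 0.30·0.70/20) = 0.129. Power is 19.1%.
- Δ = 0.37: SE₀ = 0.136, SE₁ = 0.127. Power is 79.2%.

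Both agree with the stated figures. Exact enumeration of two binomials (40 and 20) classified on the crude point estimate gives 67.4/21.6/11.0 at no effect and 22.8/23.8/53.4 at +15, against 67/22/11 and 23/24/53 in protocol Table 12.1. Every cell agrees within 1 point when the cut-offs are compared in raw floating point (≤5%, >15%). With exact handling of ties some cells miss by 4 to 10 points. The plan's figures are therefore unstratified, and the table uses point estimates only.

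**2. Point estimate under exact balance.** With 2:1 in each stratum, n₁ₛ = 2Nₛ/3 and n₀ₛ = Nₛ/3, so the Mantel-Haenszel weights n₁ₛn₀ₛ/Nₛ are proportional to Nₛ. Then Σ(Nₛ/60)(xₛ/n₁ₛ − yₛ/n₀ₛ) = Σxₛ/40 − Σyₛ/20, which is the crude difference. The probability of an estimate of at least 15 points at a true +15 was 54-55% either way.

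**3. Standard error by hand.** The documents give no response rate by stratum, so the rates below are assumptions. Take 75% in F2-F5, 30% in F6, F6 at its cap (25%), and no effect.
- Overall rate: 0.75·0.75 + 0.25·0.30 = 0.6375. Crude variance term: 0.6375·0.3625 = 0.231.
- Within-stratum term: 0.75·(0.75·0.25) + 0.25·(0.30·0.70) = 0.193.
- Multiply by 1/40 + 1/20 = 0.075 and take the root: 13.2 points crude, 12.0 points true.

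Simulation (40,000 trials; 12/33/15 subjects per stratum, so 4, 11 and 5 on placebo) gave a true SD of 12.1, a mean crude SE of 12.9 and a mean Mantel-Haenszel SE (Sato variance) of 11.7. Of the 1.2-point gap between the two SEs, 0.8 is excess in the crude SE and 0.4 is shortfall in the stratified one. At 80%/20% the true SD was 11.0, the crude SE 12.9 and crude coverage about 97%.

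**4. Interval width and test power at +15 points in every stratum.**

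| Placebo rate F2-F5 / F6 | F6 n | Crude Wald width | Mantel-Haenszel/Sato width | Change | Unstratified chi-square power | Planned CMH power |
|---|---|---|---|---|---|---|
| 30% / 30% | 15 | 0.495 | 0.495 | 0% | 20% | 20% |
| 37.5% / 7.5% | 15 | 0.496 | 0.476 | −4% | 19% | 20% |
| 70% / 30% | 15 | 0.496 | 0.459 | −7% | 21% | 26% |
| 80% / 30% | 6 | 0.412 | 0.378 | −8% | 30% | 39% |
| 80% / 30% | 15 | 0.464 | 0.400 | −14% | 23% | 34% |
| 80% / 10% (extreme) | 15 | 0.490 | 0.363 | −26% | 17% | 39% |

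An 80%/20% split falls between the last two rows: 0.478 to 0.386, −19%. Where rates differ, crude coverage was about 95-98% and Mantel-Haenszel/Sato coverage 92-94%. With equal rates both covered about 93-94%.

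**5. Missing biopsies.** The documents give no missingness rate. With 15% missing at random, independently by subject, and no imputation, crude and Mantel-Haenszel estimates fell in different 5%/15% categories in 6% of trials (37.5%/7.5%, no effect) to 15% (80%/20%, +15 points). With equal 30% rates the figure was still about 4%, so not all of the disagreement comes from stratum differences.

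**The case against.** The strongest counter-case is that this changes nothing that matters. Success rests on the point difference, which is the same either way under balance. The only planned test of response rates is already stratified by F2, F3-F5, F6. Calling the interval unstratified is an inference from silence. The obvious replacement undercovers slightly. The largest gains need high F2-F5 rates and F6 at its cap: the wider-gap scenarios imply overall placebo response well above the plan's 30%, and 37.5%/7.5%, which averages 30%, gives only 4%.

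Most of that stands, and it rules out two stronger readings.
- A reader might infer that the trial **loses power**. The documents do not support this. The gap between the power columns would arise only if an unstratified test, or the crude interval used as a test, decided the result. SAP 9.2.1 plans the CMH test.
- A reader might turn the SE ratio into **wasted subjects**: (12.1/12.9)² = 0.88 and 60/0.88 = 68, so about 8 more. This is also unsupported. The true SD of the estimate is the same under both analyses, because randomisation has already delivered the precision. Only the reported SE differs.

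Three things survive. Leaving the primary interval's method unstated is itself a gap, and with strata named in 9.2.1 but not in 9.1, crude is the natural reading. That interval is the plan's only statement of uncertainty for the primary difference. And three of the four sensitivity analyses in 9.1 (the two observed-biopsy analyses and per-protocol) use only subjects with biopsies, where exact balance cannot be assumed.

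**Conclusion.** The point holds as one of precision and specification. It does not show that the test or the decision rule fails. An unstratified interval is conservative if stratum rates differ. The stratified interval is about 4% to 14% narrower over the main assumed rates, more under sharper contrasts (19% and 26%), and no narrower if rates are equal. Roughly a third of the SE gap in the 75%/30% case is undercoverage of the Sato interval, not real gain. The guideline category for the imputed primary analysis does not change under exact 2:1 balance, but it can in the observed-biopsy and per-protocol analyses.

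This rests on assumed stratum rates and stratum sizes (only the F6 cap is documented), a constant +15 points across strata, biopsies missing at random at an assumed 15%, and no simulation of the multiple imputation.

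**What to change.** In SAP 9.1:
- Make the primary estimate the Mantel-Haenszel risk difference stratified by F2, F3-F5, F6.
- Name the stratified 95% interval, and check its coverage by simulation at the planned stratum sizes before database lock. A simple Sato Wald interval covered about 93-94%.
- Combine estimate and variance over imputations by Rubin's rules. If the chosen interval is not built from a variance (a score-type interval, for example), state how it is carried through the imputations.
- Apply the 5%/15% guideline to this estimate, in the primary and sensitivity analyses alike.
- Keep the crude difference as supportive, and state what happens if a stratum has no evaluable subjects in one arm.
- Record in 14.1 how the protocol's baseline adjustment is carried forward.

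The cost is SAP wording, a standard software option and a short coverage simulation; no new data are needed. The downside is sparse strata, with as few as 4-5 placebo subjects, and slight undercoverage if a simple Wald-type interval is kept.

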12.6.3 Efficacy Analysis

Primary Endpoint: Change from Baseline in Ishak Fibrosis Score at 2-years

The primary analysis of the primary endpoint will test the change in Ishak Fibrosis Scores at 24 months between the treatment groups in the FAS Population using ITT principles.

Subjects will be classified into one of the following 3 categories:

- Category 1. Regression at 24 months defined as a greater than or equal to a one point improvement in Ishak Fibrosis Score from Baseline.

Title: A Multicenter, Double-Blind, Randomized Trial of IDN-6556 in Subjects Who had Hepatitis C Virus (HCV) Reinfection and Liver Fibrosis or Cirrhosis following Orthotopic Liver Transplantation for Chronic HCV Infection and Who Subsequently Achieved a Sustained Virologic Response Following anti-HCV Therapy

- Category 2. Stable disease at 24 months defined as no change from Baseline in the Ishak Fibrosis Score from Baseline.
- Category 3. Progression at 24 months defined as a greater than or equal to a one point worsening from Baseline in the Ishak Fibrosis Score from Baseline or death/re-transplantation.

Changes in the Ishak Fibrosis Score at 24 months will be analyzed by a logistic regression model, appropriate for the analysis of ordinal categorical data, to derive the odds ratio and associated 95% confidence interval for IDN-6556 against placebo. The model will allow adjustment for the following variables:

- Baseline Ishak Fibrosis Score
- Immunosuppression regimen (classified into one of five groups: tacrolimus with/without steroids; cyclosporine with/without steroids; other)
- Age of the transplant donor
- Age of the recipient

Subgroup analyses of the model covariates, stated above, will also be conducted.

Shift tables of changes in Ishak Fibrosis Score over time will also be presented.

Secondary Endpoint

Estimates of the treatment effect of IDN-6556 versus placebo, and corresponding 95% confidence intervals of the modified Histological Activity Score will be conducted applying the suitable model for ordinal categorical data and detailed in the Statistical Analysis Plan. Shift tables showing changes over time will also be presented.

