14 CHANGES IN PLANNED ANALYSIS

14.1 CHANGES FROM PROTOCOL TO SAP VERSION 1.0

The primary endpoint was clarified from the protocol such that the response rate is declared as the primary endpoint to make it consistent with the sample size calculations. Response is defined per [Section 5.1](#) of this SAP.

The primary analysis was updated to reflect the primary endpoint as defined in Section 5.1. All secondary analyses will be conducted using observed cases in the FAS.

All biopsy data collected by local assessments will be captured in the database and will not be summarized or listed.

All other details provided in this SAP are intended to provide more detail and clarity to the protocol planned analyses.

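### The primary analysis can count a subject who died or was re-transplanted as a responder, because the SAP drops the protocol's progression rule for these events and imputes every missing Month 24 score

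*SAP*

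**What the plan says.** Protocol 12.6.3 sorts subjects at 24 months into regression, stable disease and progression. The last category covers "worsening from Baseline in the Ishak Fibrosis Score from Baseline or death/re-transplantation", and the synopsis has the same rule.

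SAP 5.1 replaces the three categories with a responder endpoint built on score change only:

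- "Worsening, defined as having an increase from baseline in the Ishak Fibrosis Score" (there is no death or graft-loss component)
- Response: "For subjects with baseline Ishak Fibrosis Score of F2-F5, achieving either improvement or remaining stable"
- Response: "For subjects with baseline Ishak Fibrosis Score of F6, achieving improvement"

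SAP 9.1 governs missing data for the primary estimate: "subjects with a missing Month 24 biopsy will have their Ishak fibrosis score imputed". The imputation uses age, gender, baseline score and Month 12 score, and each completed dataset is then classed by the 5.1 rule. For biopsies that exist, 9.1 says "All screening and post-baseline biopsy data collected will be used in the primary analysis, irrespective of the defined protocol visit window". One of its four sensitivity analyses is "FAS with missing M24 biopsy imputed to" non-response.

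SAP 12 only refers back to 9.1. SAP 14.1 says "The primary analysis was updated to reflect the primary endpoint as defined in Section 5.1" and does not mention the loss of the death/re-transplantation rule. In the SAP's efficacy analyses these events appear only as descriptive secondary clinical outcomes (5.2.3 and 9.2.4).

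**The concern.** A subject who has died has no Month 24 fibrosis score, and a subject whose graft was replaced no longer has the liver that was staged at baseline. The protocol treated both as the worst outcome. As written, the SAP gives the first a score predicted from subjects who were biopsied, and gives the second either such a prediction or an observed score from a different organ.

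The favorable result is not remote. Up to 15 of about 60 subjects may be F6 and need an imputed improvement. The rest are responders if the imputed score is unchanged, and protocol 4.2 says that fibrosis stabilized or regressed in most subjects after SVR.

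At stake is the difference in response rates that SAP 4 reads against 5 and 15 points. Events on placebo that are imputed as responses hide benefit. Events on emricasan that are imputed as responses hide harm. The same data feed the stratified tests in SAP 9.2.1.

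**Working it through.** **Inputs from the documents.** 40 emricasan and 20 placebo subjects (SAP 3.3); placebo response 30% (SAP 4); cut-offs at 5 and 15 points (SAP 4). The protocol's example increase is 30% to 45% (protocol 12.5), set there for regression only.

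**Inputs assumed.** Neither document gives a death or re-transplantation rate, or the probability *r* that an imputed score is a response. I take *r* = 0.3 to 0.9.

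**The plan's own table first.** Two independent binomials (n = 40 and n = 20, placebo 30%), with the difference classified at 5 and 15 points, reproduce all 21 cells of protocol Table 12.1 and SAP Table 1 within 0.5 point. At a true effect of 0 the result is 67.4/21.6/11.0% against the stated 67/22/11. At 15 it is 22.8/23.8/53.4% against 23/24/53.

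**Shift in the primary difference.** Let d1 emricasan and d0 placebo subjects die or be re-transplanted without a Month 24 biopsy. Counting them as non-response adds nothing to either rate. Imputing them adds *r* per event on average, so

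shift (SAP minus protocol rule) = 100 × *r* × (d1/40 − d0/20) points.

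| Events (emricasan, placebo) | Shift at *r* = 0.3 | Shift at *r* = 0.9 |
|---|---|---|
| 1, 0 | +0.75 | +2.25 |
| 0, 1 | −1.5 | −4.5 |
| 0, 2 | −3 | −9 |
| 4, 0 | +3 | +9 |
| 2, 1 | 0 | 0 |

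**Chance of reaching 15 points.** This is exact binomial, with 45% and 30% response among event-free subjects. Each event adds 0 (protocol rule) or *r* (SAP, average over imputations), and the top category is an estimate of at least 15 points, as in SAP Table 1.

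| Events (emricasan, placebo) | Non-response | SAP, *r* = 0.3 | SAP, *r* = 0.9 |
|---|---|---|---|
| 0, 2 | 63.8% | 48.2% | 32.8% |
| 4, 0 | 40.5% | 48.3% | 63.6% |
| 2, 1 | 52.2% | 52.2% | 52.2% |

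The SAP's responder definition includes stable disease, so true rates may be well above 30%. With an assumed 85% and 70%, two placebo events give 76.6% against 60.8% to 43.2%, and four emricasan events give 26.3% against 33.6% to 50.1%.

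**A systematic case.** Assume event rates of 15% on emricasan and 5% on placebo, and 60% response both among event-free subjects and for imputed scores. With events as non-response the true difference is 0.6 × 0.85 − 0.6 × 0.95 = 0.51 − 0.57 = −6 points, and the chance of an estimate of at least 15 points is 7.4%. Under the SAP's handling, treated as one draw, the difference is 0 and the chance is 15.3%. The excess of events on emricasan disappears from the primary result.

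**The case against.** The strongest reply has five parts.

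- **The change is allowed and mostly declared.** Protocol 12.1 lets the SAP modify the plan, 14.1 announces the responder endpoint, and protocol 8.2.1 itself defines the primary endpoint by score change without mentioning death. That stands as to permission. But 14.1 presents the change as a clarification and leaves this component out.
- **The sensitivity analyses cover it.** Setting every missing Month 24 biopsy to non-response does reclassify each subject who dies without one, SAP 9.2.1 tests that version too, and events are tabulated by arm. This is real mitigation. It does not change the primary estimate, it penalizes every missing biopsy alike, and it does not reach a re-transplanted subject who has a new-graft biopsy. How often that last case would arise is unknown.
- **The cut-offs are guidelines,** weighed with safety and other evidence (SAP 4). True, but the estimate compared with them should still be correct.
- **One-sided events are unlikely if the arms share one event rate.** At assumed common rates of 2%, 5% and 10%, the chance of at least two placebo events and no emricasan events, P(X20 ≥ 2) × P(X40 = 0), is 2.7%, 3.4% and 0.9%. The chance of at least four emricasan events and no placebo events, P(X40 ≥ 4) × P(X20 = 0), is 0.6%, 5.0% and 7.0%. This stands: chance imbalance adds error in a single trial. Systematic bias needs event rates or imputed probabilities that differ between arms.
- **The probabilities depend on ties at exactly 15 points.** SAP 4 says more than 15 in the text and at least 15 in the table. With the strict rule the non-response figures fall to 56.1% (two placebo events) and 33.0% (four emricasan events), while the SAP figures do not change. So these probabilities are uncertain by about 8 points. The per-event shifts do not depend on the tie rule.

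**Conclusion.** The concern holds. Followed as written, the SAP can count as successes the subjects whom the protocol classes as failures, and no section of the SAP states or discloses this. This rests on the text alone.

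The size is conditional. It is 1.5 to 4.5 points per placebo event and 0.75 to 2.25 points per emricasan event if the imputed response probability is 0.3 to 0.9, and zero if events are proportional to arm size with equal probabilities. Two events on placebo alone or four on emricasan alone would be enough to move an estimate across a cut-off. The category probabilities illustrate assumed scenarios and do not forecast this trial. The handling must be corrected before unblinding, because a rule for these events chosen afterwards could be chosen knowing which arm it favors.

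**What to change.** Add to SAP 5.1 and 9.1 wording such as:

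> Death or re-transplantation on or before the Month 24 biopsy date or, if no biopsy was taken, on or before the end of the planned Month 24 biopsy window (protocol 8.3), is worsening (non-response) in the primary multiple-imputation analysis and in the analysis that sets missing biopsies to non-response. Scores of these subjects are not imputed. Biopsies of a new graft are not used as Month 24 scores in any analysis.

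Keep multiple imputation for subjects not known to have died or been re-transplanted by then. Leave the observed-biopsy and per-protocol sets otherwise as they are. Protocol 8.3 gives a window of 42 days and SAP 3.5 uses 56 days for its sensitivity flag. Either could serve as the event cut-off, provided one is named in advance. List the handling in SAP 14.

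A smaller point concerns the secondary summary in SAP 5.2.3. Identify deaths also from fatal adverse-event outcome and disposition, identify re-transplants from the blinded medical review and disposition, and do not count kidney transplant as re-transplantation.

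The cost is SAP wording. Death is already a withdrawal category (protocol 8.6.2), subjects who died are listed (SAP 11.2), and re-transplants fall under the blinded review (SAP 5.2.3). Events after withdrawal may be unknown. Those subjects stay in the imputation, so the result depends to that extent on follow-up, and their number should be reported by arm.
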